9.0 Ancillary Treatment/Supportive Care/Concomitant Medications

9.1 Diarrhea

Due to frequent reports of diarrhea with AZD1775 administration, anti-diarrhoeal treatment with loperamide (Imodium) is required at the **first** onset of diarrhea according to American Society of Clinical Oncology (ASCO) guidelines. Oral loperamide 4mg should be administered at the first onset of diarrhoea and then 2mg every 2 hours until patient is diarrhea-free for at least 12 hours. The first dose of loperamide could be lowered to 2mg if the diarrhea is recurrent and if, in the opinion of the treating physician, the diarrhoea is not severe. The dose of loperamide should not exceed 16mg in a 24-hour period.

Patients should be instructed to notify the Investigator or research staff of the occurrence of bloody or black stools, symptoms of dehydration, fever, inability to take liquids by mouth, and inability to control diarrhoea within 24 hours of using loperamide or other prescribed anti-diarrheal medications

If diarrhea is severe (i.e., requiring intravenous [IV] rehydration) and/or associated with fever or severe neutropenia (Grade 3 or 4), broad-spectrum antibiotics must be prescribed. Patients with severe diarrhea or any diarrhea associated with severe nausea or vomiting should be hospitalised for IV hydration and correction of electrolyte imbalances.

Nausea and vomiting

All patients must receive a 5-HT3 antagonist, ondansetron (Zofran) 8 mg PO QD or granisetron (Kytril) 1 mg PO QD prior to each dose of AZD1775. If nausea and vomiting continue, a second dose of antiemetics can be taken 8 hours later if necessary. In addition, dexamethasone 4 mg PO may be given with each AZD1775 dose unless contraindicated or not well-tolerated. Dexamethasone or the 5-HT3 antagonist may be given by IV route as needed.

Promethazine (Phenergan), prochlorperazine (Compazine), and benzodiazepine may still be used as additional adjunctive treatments during AZD1775 therapy.

Please note: aprepitant [Emed] and fosaprepitant are not permitted due to known DDIs.

Patients should be encouraged to maintain liberal oral fluid intake.

Suitable alternative medications may be used, with adequate justification, in those studies where the use of any of the above medications might interfere with other study procedures or are deemed insufficient.

Febrile neutropenia

Patients experiencing febrile neutropenia with significant symptoms should be managed in a hospital setting according to standard procedures, with the urgent initiation of IV antibiotic therapy. Patients with febrile neutropenia without symptoms should be managed according to standard guideline.

Routine use of colony-stimulating factors (G-CSF or GM-CSF) is not recommended. Prophylactic use of colony-stimulating factors should be discussed with the study chair. Therapeutic use in patients with serious neutropenic complications may be considered at physician discretion. Recombinant erythropoietin to maintain adequate hemoglobin levels is discouraged and only allowed after discussion with the study chair.

- 9.2 Patients should receive full supportive care while on this study. This includes blood product support, antibiotic treatment and treatment of other newly diagnosed or concurrent medical conditions. All blood products and concomitant medications such as antidiarrheals, analgesics, anti-emetics received from the first administration of study drugs until 30 days after the final dose are to be recorded in the medical record. For more severe diarrhea (i.e. Grade 3 or 4) supportive measures such as hydration and anti-diarrheals are recommended according to institutional practice guidelines and as deemed appropriate by the medical situation (i.e. IV rehydration as in- or outpatient, antibiotics).
- 9.3 Anti-emetic therapy (excluding aprepitant) may be used in accordance with standard practice and/or the discretion of the investigator.
- 9.4 Hydroxyurea is allowed during the trial to control blast counts/WBC if the patient is felt to derive benefit from study treatment.
- 9.5 Antifungal treatment on protocol: The preferred azole anti-fungal medication is Fluconazole, (alternatively Posaconazole may be given (same below criteria apply for posaconazole) which can be given during treatment with AZD1775 at the treating physician's discretion, however with dose reductions of AZD1775 as outlined below. Based on the DDI simulations with Fluconazole (moderate inhibitor), there is an approximately 35% increase in AZD1775 exposure. Therefore if Fluconazole (or Posaconazole) are given the following AZD1775 dose reductions need to be followed:
- AZD1775 200 mg dose → reduce to AZD1775 150 mg
 AZD1775 250mg dose → reduce to AZD1775 200 mg
 AZD1775 300mg dose → reduce to AZD1775 250mg

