11.2 MDS and CMML response criteria

Category	Hematologic Response Response Criteria (responses must last at least 4 weeks) ^a
Complete remission (CR)	Bone marrow: $\leq 5\%$ myeloblasts with maturation of all cell lines. If present, persistent dysplasia will be noted (dysplastic changes should consider the normal range of dysplastic changes.) Peripheral blood: 
 • Hemoglobin (Hgb) ≥ 11 g/dL (untransfused, patient not on erythropoietin) • Neutrophils $\geq 1.0 \times 10^9/L$ (not on myeloid growth factor) • Platelets $\geq 100 \times 10^9/L$ (not on a thrombopoietic agent) • Blasts 0%;
Partial remission (PR)	All CR criteria (if abnormal prior to treatment), except: Bone marrow blasts decreased by $\geq 50\%$ compared with pretreatment but still $> 5\%$. Cellularity and morphology not relevant.
Marrow CR	Bone marrow: $\leq 5\%$ myeloblasts and decrease by $\geq 50\%$ over pretreatment if $> 10\%$ at baseline Peripheral blood: if hematologic improvement (HI) responses, they will be noted in addition to the marrow CR
Stable disease (SD)	Failure to achieve at least PR, but no evidence of progression for > 8 weeks.
Failure	Death during treatment or disease progression characterized by worsening of cytopenias, increase in percentage of bone marrow blasts, or progression to an MDS FAB subtype more advanced than pretreatment after 6 months/cycles of therapy
Relapse after CR or PR	At least one of the following: 
 • Return to pretreatment bone marrow blast percentage • Decrement of $\geq 50\%$ from maximum remission/response levels in granulocytes or platelets • Reduction in hemoglobin concentration by ≥ 1.5 g/L or transfusion dependence if previously had become transfusion independent for > 8 weeks.
Cytogenetic response	Complete: Disappearance of the chromosomal abnormality without appearance of new ones Partial:

	At least 50% reduction of the chromosomal abnormality

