Disease progression	
For patients with:
 
 • Less than 5% blasts: $\geq 50\%$ increase in blasts to $> 5\%$ blasts • 5%-10% blasts: $\geq 50\%$ increase in blasts to $> 10\%$ blasts • 10%-20% blasts: $\geq 50\%$ increase in blasts to $> 20\%$ blasts • 20%-30% blasts: $\geq 50\%$ increase in blasts to $> 30\%$ blasts 
Any of the following:
 
 • At least 50% decrement from maximum remission/response levels in granulocytes or platelets • Reduction in hemoglobin concentration by ≥ 2 g/dL • Transfusion dependence if previously had become transfusion independent for > 8 weeks^c
a	For a designated response (CR, PR), relevant response criteria must be noted on at least 2 successive determinations at least 1 week apart after an appropriate period following therapy (e.g., 1 month or longer).
c	In the absence of another explanation, such as acute infection, gastrointestinal bleeding, hemolysis, etc.

Hematologic Improvement*	Response Criteria (responses must last at least 8 weeks)^a
Erythroid response (pretreatment, Hgb < 11 g/dL)	Hgb increase by ≥ 1.5 g/dL Relevant reduction of units of red blood cell (RBC) transfusions by an absolute number of at least 4 RBC transfusions/8 wk compared with the pretreatment transfusion number in the previous 8 wk. Only RBC transfusions given for an Hgb of ≤ 9.0 g/dL pretreatment will count in the RBC transfusion response evaluation.
Platelet response (pretreatment, $< 100 \times 10^9/L$)	Absolute increase of $\geq 30 \times 10^9/L$ for patients starting with $> 20 \times 10^9/L$ Increase from $< 20 \times 10^9/L$ to $> 20 \times 10^9/L$ and by at least 100%
Neutrophil response (pretreatment, $< 1.0 \times 10^9/L$)	At least 100% increase and an absolute increase $> 0.5 \times 10^9/L$.
Progression or relapse after HI	At least 1 of the following: 
 • At least 50% decrement from maximum response levels in granulocytes or platelets • Reduction in Hgb by ≥ 1.5 g/dL • Transfusion dependence^b

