11.3 Response Criteria for MF

Response categories	Required criteria (for all response categories, benefit must last for ≥12 weeks in order to qualify as a response)
Complete Remission (CR)	Bone marrow: * Age-adjusted normocellularity; <5% blasts; ≤Grade 1 myelofibrosis**, AND Peripheral blood: Hemoglobin ≥100 g/L and <UNL; Neutrophil count ≥1 x 10 ⁹ /L and <UNL; Platelet count ≥100 x 10 ⁹ /L and <UNL; <2% immature myeloid cells***, AND Clinical: Resolution of disease symptoms; Spleen and liver not palpable; No evidence of EMH
Partial Remission (PR)	Peripheral blood: Hemoglobin ≥100 g/L and <UNL; Neutrophil count ≥1 x 10 ⁹ /L and <UNL; Platelet count ≥100 x 10 ⁹ /L and <UNL; <2% immature myeloid cells***, AND Clinical: Resolution of disease symptoms; Spleen and liver not palpable; No evidence of EMH OR Bone marrow: * Age-adjusted normocellularity; <5% blasts; ≤Grade 1 myelofibrosis**, AND Peripheral blood: Hemoglobin ≥85 but <100 g/L and <UNL; Neutrophil count ≥1 x 10 ⁹ /L and <UNL; Platelet count ≥50 but <100 x 10 ⁹ /L and <UNL; <2% immature myeloid cells***, AND Clinical: Resolution of disease symptoms; Spleen and liver not palpable; No evidence of EMH
Clinical improvement (CI)	The achievement of anemia, spleen or symptoms response without progressive disease or increase in severity of anemia, thrombocytopenia or neutropenia‡
Anemia response	Transfusion-independent patients: a ≥20 g/L increase in hemoglobin level† Transfusion-dependent patients: becoming transfusion-independent††
Spleen response§	A baseline splenomegaly that is palpable at 5-10 cm, below the LCM, becomes not palpable§§, OR A baseline splenomegaly that is palpable at >10 cm, below the LCM, decreases by ≥50%§§ A baseline splenomegaly that is palpable at <5 cm, below the LCM, is not eligible for spleen response Confirmation by MRI or CT showing ≥35% spleen volume reduction is recommended (but not required)
Progressive disease¥	Appearance of a new splenomegaly that is palpable at least 5 cm below the LCM, OR A ≥100% increase in palpable distance, below LCM, for baseline splenomegaly of 5 to 10 cm, OR A 50% increase in palpable distance, below LCM, for baseline splenomegaly of >10 cm, OR Leukemic transformation confirmed by a bone marrow blast count of ≥20%, OR A peripheral blood blast content of ≥20% associated with an absolute blast count of ≥1 x 10 ⁹ /L that lasts for at least two weeks

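### Erythropoietin is permitted on study, but the MDS erythroid improvement and MF anemia response criteria do not exclude hemoglobin gains that it produces

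*Combined protocol and SAP*

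**What the plan says.** **Permission.** The febrile neutropenia paragraph of Section 9.1 says of erythropoietin: "Recombinant erythropoietin to maintain adequate hemoglobin levels is discouraged and only allowed after discussion with the study chair". On colony-stimulating factors it says "Routine use of colony-stimulating factors (G-CSF or GM-CSF) is not recommended", asks for discussion with the study chair before prophylactic use, and adds "Therapeutic use in patients with serious neutropenic complications may be considered at physician discretion".

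**Where the response criteria guard against this.** In the Section 11.2 table, complete remission requires "Hemoglobin (Hgb) ≥ 11 g/dL (untransfused, patient not on erythropoietin", and the neutrophil count must be reached "not on myeloid growth factor". Partial remission takes over the complete-remission criteria apart from the blast condition, so it inherits both.

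**Where they do not.** The erythroid improvement row of Section 11.2 asks for "Hgb increase by ≥ 1.5 g/dL" or a reduction of at least four red-cell transfusions per 8 weeks. The MF anemia response in Section 11.3 asks for "a ≥20 g/L increase in hemoglobin level" in transfusion-independent patients, or for transfusion independence in dependent ones. Neither row, nor its footnotes, mentions erythropoietic agents.

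**The concern.** Section 9.1 describes erythropoietin as given to keep hemoglobin adequate. That is the quantity the erythroid and anemia criteria measure. If a patient starts the agent on study and hemoglobin rises or transfusions stop, the criteria cannot separate that effect from an effect of AZD1775.

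The authors evidently saw the problem, because they wrote the exclusion into the MDS complete-remission row. With the condition in one row and absent from others, an analyst applying the tables as printed would score the supported value as a response.

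Two reported results are exposed. MDS hematologic improvement belongs to secondary goal 2.22 and is summarized under Section 16.42. MF anemia response can by itself give clinical improvement, which counts toward best overall response under primary goal 2.13.

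**Working it through.** The plan states no figure on this point, so the main check is a comparison of the criteria, followed by simple arithmetic for the MF cohort.

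**1. Criteria side by side**

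| Criterion | Serves | Minimum duration | Growth-factor condition |
|---|---|---|---|
| MDS complete remission (11.2) | CR/CRi endpoint | 4 weeks | Yes, explicit |
| MDS partial remission (11.2) | response category | 4 weeks | Yes, inherited |
| MDS erythroid improvement (11.2) | goal 2.22 | 8 weeks | None |
| MDS neutrophil improvement (11.2) | goal 2.22 | 8 weeks | None |
| MF anemia response (11.3) | goal 2.13, through clinical improvement | 12 weeks | None |

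**2. Is there a rule elsewhere that fills the gap?** I found none.
- The improvement footnotes in Section 11.2 require baseline counts free of transfusion influence. The allowance for another explanation is attached to losing a response, not to gaining one.
- The MF footnotes deal with transfusions before baseline and define transfusion independence as a rolling 12-week interval without red cells, ending at a hemoglobin of at least 85 g/L. They do not mention erythropoietin.
- Section 16.21 refers generally to standard criteria, but reproduces no growth-factor condition from them. Section 16.42 gives summary statistics only.
- Section 9.2 has concomitant medications recorded, and Section 19.1 has them entered in the trial database. Neither links them to response scoring.

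**3. Size in the MF cohort.** Section 16.1 plans n = 7, so one reclassified patient moves the rate by 1/7 = 14.3 points. Exact (Clopper-Pearson) 95% intervals:
- 0/7 = 0%: upper limit 1 − 0.025^(1/7) = 0.410, so 0 to 41.0%.
- 1/7 = 14.3%: 0.4 to 57.9%.
- 2/7 = 28.6%: 3.7 to 71.0%.

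For scale, Section 1.1 puts response rates to current therapies in advanced MF below 5-10%.

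**4. Illustration under assumption.** Let p be the true response rate and q the share of true non-responders scored as responders because of erythropoietin. The documents do not give q, so the values below are assumptions. For p, I use 5% and 10%. The apparent rate is p + (1 − p)q, and the chance of at least one false responder among 7 is 1 − [1 − (1 − p)q]^7.

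| q (assumed) | Apparent rate, p = 5% to 10% | Chance of at least one false responder in 7 |
|---|---|---|
| 5% | 9.8% to 14.5% | 28% to 29% |
| 10% | 14.5% to 19.0% | 48% to 50% |
| 20% | 24.0% to 28.0% | 75% to 77% |

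These rows show sensitivity to q. They are not a forecast.

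**5. Do the decision rules depend on these criteria?** The Section 16 rules count CR plus CRi only. Their tabulated probabilities reproduce from the binomial distribution:
- Arm A, at least 6 of 21: 0.083 at 15% (stated 0.08) and 0.904 at 40% (stated 0.90).
- Arms B and C, at least 3 of 20: 0.076 at 5% (stated 0.08) and 0.909 at 25% (stated 0.91).

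Neither hematologic improvement nor MF clinical improvement enters these calculations.

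**The case against.** The strongest reply is that the exposure is narrow and the consequences limited, and much of it stands.

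- **Use is restricted.** Erythropoietin is discouraged and must first be discussed with the study chair. That makes cases fewer, but the discussion has no bearing on how the response is then scored.
- **Duration rules screen out short courses.** Improvement must last 8 weeks and an MF response 12. This largely disposes of brief therapeutic G-CSF as a route to neutrophil improvement. It does not dispose of sustained erythropoietin.
- **The MF cohort is a descriptive pilot.** It has seven patients and no decision rule, and is kept out of the Arm C analysis. The 0/7 and 1/7 intervals overlap almost entirely, and any misclassified patient would move the rate by 14.3 points. All true, but goal 2.13 is listed as primary, and the reported rate should not include responses that another drug could explain.
- **A blanket non-responder rule would go too far.** I found no eligibility criterion in Section 3 that names erythropoietic agents. A patient may therefore enter on a stable dose, and a rise above an on-agent baseline is not explained by starting the agent. This stands, and the fix allows for it.

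A reader might also infer more than the documents support:

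- **AML and the primary endpoint.** G-CSF cannot lift AML partial remission to CR or CRi by raising counts. Section 11.1 already requires count recovery for partial remission, which is separated from CR by marrow blasts. A move from CRi to CR changes nothing, since both are successes. The remaining route, from morphologic leukemia-free state to CRi, requires CRi to mean exactly one unrecovered count, which Section 11.1 does not say.
- **Platelets.** The growth-factor text in Section 9.1 does not mention thrombopoietic agents, so it gives no basis for a platelet concern.
- **MF complete or partial remission.** Every route also requires resolved symptoms, a non-palpable spleen and liver, and no extramedullary hematopoiesis. Raising counts does not supply these.

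**Conclusion.** The gap is real and confined to two criteria: MDS erythroid improvement (goal 2.22) and MF anemia response (goal 2.13, through clinical improvement). Followed exactly, the tables score an erythropoietin-driven gain as a response to AZD1775. This is more than missing detail, because a stated scoring rule can return a wrong classification.

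Each affected MF patient adds 14.3 points to a rate based on seven. The overall bias depends on how many patients start or increase erythropoietin on study and meet the duration rule, and the documents give no figure for either. For MDS the size therefore stays unknown.

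The conclusion assumes that the printed rows of Section 11 are the operative ones. It does not extend to the sample sizes, the stated power, or the CR/CRi decision rules for Arms A to C, none of which is shown to be affected.

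**What to change.** This changes scoring only. Who may receive these agents is left as it is.

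1. In the Section 11.2 erythroid improvement row and the Section 11.3 anemia response, state that values or transfusion-free intervals obtained after an erythropoietic agent is started or increased on study cannot support the response unless the criterion is also met off the agent. This extends the condition already used for MDS complete remission. It leaves patients on a stable pre-study agent assessable against their own baseline.
2. For consistency, add the matching myeloid growth factor condition to the neutrophil improvement row.
3. Derive the flag from the concomitant-medication data recorded under Section 9.2 and entered under Section 19.1. Section 9.2 starts recording at the first study dose, so baseline use and dose should be captured as well, with start, change and stop dates.
4. Settle the rule before responses are summarized, so that cases are not judged one by one.

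The cost is a footnote in two tables, one derivation in the analysis program and, if not already collected, a baseline field. A few users may no longer be scored as responders, so the reported improvement rates could be slightly less favourable. No sample size or decision boundary changes.

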1.43 Clinical Pharmacokinetics and pharmacodynamics

Clinical Pharmacokinetics

The PK data of AZD1775 following a single oral administration showed a moderate rate of absorption with a T_{max} occurring at 3 to 4 hours. Post-peak plasma concentrations declined essentially in a mono-exponential manner with a t_{1/2} in the region of 10 hours. Exposure as measured by maximum plasma drug concentration observed (C_{max}) and area under the curve (AUC 0-∞) increased in a dose-proportional manner over the dose range of 325 to 1300 mg. The urinary excretion of AZD1775 was investigated after single-oral-dose monotherapy at 325, 650, and 1300 mg of AZD1775. The mean percent of total AZD1775 excreted unchanged in urine over a 24-hour period was 5.15% to 11.9%, which is comparable to what was observed in preclinical species (urinary excretion as unchanged drug in rats and dogs were ~8.6% and 11.8% of the dose, respectively, over a 48-hour collection interval). The mean renal clearance of AZD1775 at 325 mg was approximately 2.30 L/hour (38.3 mL/minute), below that expected due to filtration alone (based on an AZD1775 unbound fraction of 39.5% and a typical glomerular filtration rate of 120 mL/minute) of 47.4 mL/minute, indicating that net reabsorption appeared to be taking place. Overall, the results suggest that urinary excretion is not the major route of AZD1775 elimination.

Following single (100 to 325 mg) and multiple dose administrations of AZD1775 (25 to 325 mg BID and 100 to 200 mg once daily [QD]) with carboplatin, cisplatin, and gemcitabine, plasma exposure of AZD1775 was consistent with predictions based on the single-dose regimen. The median T_{max} values were between 1.02 and 4.25 hours. Given a t_{1/2} of approximately 10 hours, steady-state was expected to be achieved after approximately 3 days of AZD1775 treatment in adult patients. Accumulation ratios for AZD1775 BID doses (geometric mean ratio = Day 3/Day 1) for the area under the plasma-concentration time curve from time 0 to 8 hours post dose (AUC_{0-8hr}), C_{max}, and plasma drug concentration observed at 8 hours post dose (C_{8hr}) averaged 0.991 to 3.82, 0.928 to 3.32, and 1.01 to 2.98, respectively, across tested AZD1775 BID doses in combination with gemcitabine, cisplatin, and carboplatin.

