In this case, a written statement outlining drug dosage, method of administration, follow-up tests required, and telephone number to call to discuss any questions with the responsible investigator must be sent with the patient to provide necessary information to the LMD, post cycle 1 of treatment therapy. The LMD will be required to supervise the administration of the study drugs as stipulated in the protocol and provide written documentation that the drug was administered.

8.0 Dosage Modification Based on Adverse Events - If multiple adverse events are seen, administer dose based on greatest reduction required for any single adverse event observed. Dose modifications apply to the treatment given in the preceding cycle and are based on adverse events observed since the prior dose. Dose modification recommendations listed below are general guidelines, and appropriate dose adjustments for patient safety should be done if needed per treating physician discretion.

ALERT: ADR reporting may be required for some adverse events. See Section 10.0.

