In vitro data has shown that AZD1775 is metabolised predominantly by CYP3A4, with an FMO3 and/or FMO5 component. As a result, there is potential for the exposure of AZD1775 to be effected by drugs which inhibit or induce the metabolism of CYP3A4. In the clinic, coadministration of AZD1775 with the moderate CYP3A4 inhibitor, aprepitant, resulted in a 40% increase in the plasma levels of AZD1775. Drugs known to be moderate to strong inhibitors/inducers of CYP3A4 are therefore prohibited for use in the current study, including aprepitant.

In vitro data suggests that AZD1775 may be a weak reversible inhibitor of CYP2C19 (IC₅₀ 12 µM).

Caution should therefore be exercised when AZD1775 is coadministered with agents that are sensitive substrates of CYP2C19, or substrates of this enzyme with a narrow therapeutic range.

Based on in vitro studies, AZD1775 has been show to be a weak reversible inhibitor (IC₅₀ 14 µM) and a time-dependent inhibitor of CYP3A4 (K_{inact} 0.061/min, K_i 6.04 µM). The full impact of the time dependent inhibition is currently unknown, however, modelling data has predicted an 8-10 fold increase in the exposure of sensitive CYP3A4 substrates when administered with AZD1775 (250 mg BID for 5 doses). To date, no significant DDI effects have been reported in the clinic that may be related to the TDI finding. However, sensitive CYP3A4 substrates or substrates of CYP3A4 with a narrow therapeutic window are prohibited.

AZD1775 has been shown to be a weak inducer of CYP1A2 in vitro (39% increase in activity of positive control). Given the nature of the AZD1775 dosing schedule, however, the risk of induction in the clinic is considered low. No specific precautions are recommended at this time, except to be initially vigilant when using substrates of CYP1A2 with a narrow therapeutic range.

Transporter studies (in vitro) have shown that AZD1775 is both a substrate and inhibitor (IC₅₀ 20 µM) of P-gp. Maximum impact of these finding is likely to occur for drugs administered orally at the same time as AZD1775. Caution should therefore be exercised when agents that are inhibitors or substrates of P-gp are administered concomitantly with AZD1775.

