Recent invitro transporter studies have shown AZD1775 to be an inhibitor of BCRP (IC₅₀ 5.1 µM). This finding is particularly relevant for drugs administered orally where exposure is normally limited by BCRP-mediated efflux, in particular some statins. Modelling has predicted a substantial increase in the exposure of Atorvastatin when coadministered with AZD1775 and the use of Atoravastatin is therefore prohibited in the current study. Other drugs where the disposition is mediated via BCRP should be administered with caution, dose modification considered or substituted by an alternative drug.

Herbal preparations/medications can be substrates, inhibitors and inducers, similar to any registered medication. Herbal preparations are therefore not allowed throughout the study. These herbal medications include, but are not limited to: St. John's wort, kava, ephedra (ma huang), ginkgo biloba, dehydroepiandrosterone (DHEA), yohimbe, saw palmetto, and ginseng.

In addition, any other drugs should be avoided at the Investigator's discretion if, in their opinion, the co-administration with AZD1775 may increase the risk of a clinically significant drug interaction.

A list of the main CYP3A4 substrates, inhibitors (strong and moderate) and inducers, CYP2C19 substrates, P-gp substrates and inhibitors and BCRP substrates are shown below. This is not an exhaustive list and further details can be found at Expert Opin. Drug Metab. Toxicol. (2013) 9(6):737-751.

CYP3A4 Inhibitors**Strong**

Boceprevir	Ketoconazole
Clarithromycin	LCL161
Cobicistat (GS-9350)	Lopinavir
Conivaptan	Mibefradil
Danoprevir	Nefazodone
Elvitegravir	Nelfinavir
Fosamprenavir	Posaconazole
Grapefruit juice	Ritonavir
Idelalisib	Saquinavir
Indinavir	Telaprevir
Itraconazole	Telithromycin
	Tipranavir
	Troleandomycin
	Voriconazole

Moderate

ACT-178882	Imatinib
Amprenavir	Ledipasvir
Aprepitant	Lomitapide
Atazanavir	Netupitant
Casopitant	Schisandra sphenanthera
Ciprofloxacin	Tofisopam
Crizotinib	Verapamil
Darunavir	
Dronedarone	
Diltiazem	
Erythromycin	
FK1706	
Fluconazole*	
Fosamprenavir	

*The preferred azole anti-fungal medication is Fluconazole, alternatively Posaconazole may be given. For dose modification see section 9.5.

CYP3A4 Inducers (Strong and Moderate)

Avasimibe	Nafcillin
Bosentan	Phenobarbital
Carbamazepine	Phenytoin
Efavirenz	Rifabutin
Enzalutamide	Rifampin

Etravirine	Ritonavir
Genistein	Semagacestat
Lersivirine	St John's Wort
Lopinavir	Thioridazine
Mitotane	Tipranavir
Modafinil	

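### Section 9.5 requires for posaconazole, a strong CYP3A4 inhibitor in Appendix VI, the 50 mg AZD1775 reductions derived only from a fluconazole (moderate inhibitor) simulation

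*Combined protocol and SAP*

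**What the plan says.** Section 9.5 makes fluconazole the preferred azole and posaconazole the alternative, both at the treating physician's discretion. Its pharmacological basis is one sentence: "Based on the DDI simulations with Fluconazole (moderate inhibitor), there is an approximately 35% increase in AZD1775 exposure". From this it concludes that "if Fluconazole (or Posaconazole) are given the following AZD1775 dose reductions need to be followed", and lists 200 to 150, 250 to 200 and 300 to 250 mg. A parenthesis adds that the "same below criteria apply for posaconazole". There is no line for a patient already at 150 mg, although that is level -1 in Table 7.21 and level -3 in Table 7.31.

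Appendix VI places posaconazole in its strong CYP3A4 inhibitor list and fluconazole in its moderate list. A footnote there repeats that "The preferred azole anti-fungal medication is Fluconazole, alternatively Posaconazole may be given" and refers to 9.5 for dosing. The note under exclusion criterion 3.30b says the same. Appendix VI otherwise prohibits moderate and strong CYP3A4 inhibitors. No section reports an exposure change with posaconazole or any other strong inhibitor, and Appendix VI states that formal interaction studies have not been done.

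**The concern.** A reduction sized on a moderate inhibitor is made compulsory for a drug that the protocol itself puts in the stronger class. If posaconazole blocks CYP3A4 more than fluconazole does, a patient dosed exactly as 9.5 instructs receives more AZD1775 than the nominal dose level intends.

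The protocol treats changes of this size as relevant. Section 15.16 says that the 40% rise seen with aprepitant, a moderate inhibitor, may matter clinically at the chosen MTDs, and aprepitant is banned. The 300 mg step, the smallest in proportion, applies at Arm C's presumed expansion dose (Table 8.12).

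Exposed patients are foreseeable, because the note to 3.21 admits patients whose infection is controlled on antifungals. In the safety portion an interaction-driven toxicity would also count toward the MTD. Section 7.4a has no exception for it, and two DLTs in six patients mean the MTD has been exceeded (7.53).

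**Working it through.** **Inputs.** From 9.5: dose pairs 200/150, 250/200 and 300/250 mg, and a simulated fluconazole rise of 35%. The 35% cannot be reproduced, because the simulation inputs are not given. From 15.16 and Appendix VI: an observed aprepitant rise of 40%. Assumption: exposure is proportional to dose. Section 1.43 says exposure "increased in a dose-proportional manner over the dose range of 325 to 1300 mg", which lies above the study doses. It also reports exposure at lower doses with chemotherapy, including 100 to 200 mg once daily, as consistent with single-dose predictions.

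**Largest rise each step fully offsets** = nominal dose / reduced dose − 1.

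- 200/150 − 1 = 0.333, or 33%
- 250/200 − 1 = 0.25, or 25%
- 300/250 − 1 = 0.20, or 20%

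All three are below 35%. A fixed 50 mg step removes a smaller share of a larger dose, so the protection is least at 300 mg.

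**Exposure after the step, relative to nominal** = (reduced / nominal) × (1 + rise).

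| Step (mg) | Rise 35% (fluconazole) | Rise 40% (as aprepitant) |
|---|---|---|
| 200 to 150 | 150 × 1.35 / 200 = 101% | 150 × 1.40 / 200 = 105% |
| 250 to 200 | 200 × 1.35 / 250 = 108% | 200 × 1.40 / 250 = 112% |
| 300 to 250 | 250 × 1.35 / 300 = 112.5% | 250 × 1.40 / 300 = 116.7% |

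Exact parity at 35% would need 200/1.35 = 148, 250/1.35 = 185 and 300/1.35 = 222 mg. On a 50 mg grid the fluconazole steps are a reasonable rounding and are not challenged here.

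**Posaconazole.** If it inhibits CYP3A4 at least as much as fluconazole, which is an assumption drawn from the Appendix VI classes, the 35% column is a lower bound. No upper bound follows from the documents. Appendix VI says "AZD1775 is metabolised predominantly by CYP3A4, with an FMO3 and/or FMO5 component", and 1.43 reports 5.15% to 11.9% of the drug unchanged in urine. These routes limit the possible rise, but the documents do not say how far, or whether the fluconazole simulation modelled them.

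**The case against.** The strongest reply is that no additional harm has been quantified. The only computed excess is the fluconazole one, which is accepted, and the posaconazole effect is unknown. That is correct, and it limits what can be claimed.

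Permission is also deliberate: it appears in 9.5, the 3.30b note and Appendix VI, and posaconazole is second choice. A reader might infer that the protocol contradicts itself by allowing a prohibited drug. It does not, because the exception is explicit. A reader might also infer that no posaconazole simulation was ever done. The documents show only that none is stated, and they refer to an Investigator's Brochure that is not available here.

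Safeguards exist. Section 8.0 says "appropriate dose adjustments for patient safety should be done if needed per treating physician discretion". Section 14.1 requires a PK profile on Cycle 1 Day 5, with pre-dose samples on Cycle 2 Day 5 and Day 5 of later odd cycles. Section 7.4b promises real-time PK and/or PD review during escalation in Arms A and B, and 16.8 monitors DLTs continuously. AML patients have laboratory tests at least twice weekly and ECGs at least weekly in Cycle 1. Dosing covers only 10 days per cycle, with a half-life near 10 hours. These limit undetected over-exposure. They are mostly reactive, however: the full profile comes after about five days of dosing, and none of them sets a posaconazole dose.

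It is also tempting to demand a cut of at least two dose levels. The documents do not support that. Such a minimum comes from the 50 mg grid, not from posaconazole data, and 250 to 150 mg would fall below the lowest AZD1775 level in Table 8.11 (200 mg). If the true rise were 35%, it would leave 200 × 1.35 / 300 = 90% or 150 × 1.35 / 250 = 81% of nominal exposure.

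**Conclusion.** The concern holds as a fault in a stated dosing rule. By the protocol's own inhibitor classes, 9.5 applies a moderate-inhibitor correction to a strong inhibitor. That correction has no reserve: it offsets rises of 33%, 25% and 20% against a fluconazole rise of about 35%. Exposure on posaconazole would be at least 101%, 108% and 112.5% of nominal at the three levels. This rests on two assumptions: dose proportionality below 325 mg, and inhibition by posaconazole at least equal to fluconazole's.

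A reader might go further. Section 1.51 puts the once-daily single-agent MTD at 300 mg and the DLT level at 400 mg, and a 1.6-fold rise after the 300 to 250 mg step would equal 400 mg (250 × 1.6). The documents do not support saying that posaconazole reaches this. They neither show nor exclude a rise of that size. The finding is a missing justification and an absent margin in a compulsory rule, not a demonstrated overdose. It should be corrected, with medium confidence about its practical importance.

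**What to change.** 1. Limit the 9.5 table to fluconazole, with its steps unchanged.
2. Allow posaconazole only when fluconazole or a non-azole is unsuitable, with Medical Monitor agreement. Set a posaconazole-specific AZD1775 dose before co-dosing, from a simulation that includes the FMO and renal routes. Check it against the PK in 14.1.
3. Amend the note under 3.30b and the Appendix VI footnote to match.
4. State a rule for patients already at 150 mg: use a non-azole, or refer to the Medical Monitor.
5. State that an azole reduction does not count toward the two-reduction limit in 8.3 and is reversed when the azole stops, as an explicit exception to the ban on re-escalation there.

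The cost is one amendment and one simulation, with no change to sample size or DLT rules. The Cycle 1 Day 5 profile is already mandatory. Checking posaconazole started later would add one six-sample profile per patient. Physicians lose some freedom to use posaconazole, and moving a patient whose infection is controlled on it carries a clinical cost. If its true effect is close to fluconazole's, a larger cut may modestly under-expose patients in a trial whose primary endpoint is CR/CRi.
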